7.2.5 Selection of Antidepressant by Specialty Analysis

- To understand the antidepressant choice among the Korean providers by specialty
- Secondary analysis
- Endpoints:
 - Proportion of 11 antidepressants by provider specialty
- Population: patients who satisfies the acute treatment phase population and with a prespecified comorbidity
- Significance on continuous variables will be tested by ANOVA (if equal variance condition satisfied) or Kruskal-Wallis H test (otherwise). Provider specialty and other patient characteristics will be used to fit antidepressant choice by multivariate logistic regression analysis of each study drug choice.
- Covariates: antidepressant class covariates such as SSRIs, SNRIs, other ADs will be used as grouping variables. Provider specialty and other patient characteristics will be used to fit antidepressant choice by multivariate logistic regression analysis of each study drug choice.
- Missing values will be dropped from the analysis.
- The role of this analysis is to provide information on antidepressant selection in the acute phase of drug therapy for Korean patients with depression and comorbidity by each comorbidity group.

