9.7. Data analysis

The proportions and drug utilization patterns comparisons of 11 study drugs will use all the patients satisfying inclusion and exclusion criteria (raw data). Adherence, persistence, discontinuation, recurrence, and adverse outcomes comparison of 11 study drugs will use both raw data and matched data where patients will be matched on demographic and clinical characteristics. All outcome variables will be summarized *descriptively* through the tabular and graphical display of mean values, medians, ranges and standard deviations of continuous variables of interest and frequency distributions of categorical variables. Safety outcomes of treatments will be estimated from time-to-event models. The 95% confidence intervals for the estimates will be calculated and $p < 0.05$ will be considered significant. All analyses will be carried out using SAS version 9.4 which is installed on HIRA server. Analysis and reporting will be compliant with Strengthening the Reporting of Observational Studies in Epidemiology (STROBE) recommendations.

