2.2 STUDY OBJECTIVES

Primary objectives:

1. Explore baseline characteristics and drug utilization patterns of 11 commonly used antidepressant therapy during 90 days of acute treatment phase
 - Top 11 commonly used antidepressants according to local market data are as follows:
 - Escitalopram, paroxetine, fluoxetine, mirtazapine, duloxetine, sertraline, venlafaxine, tianeptine, vortioxetine, desvenlafaxine, bupropion
 - Proportion of antidepressants prescribed by sex, age (<20, 21-64, > 65), sex and age combined
 - Initial doses used, average daily doses of each antidepressants
 - Average length of treatment with index medication before therapy change occurs (switching, combination, augmentation, discontinuation)
 - Adherence and persistence measured by medication possession ratio during first 90 days of treatment period
2. Explore drug utilization patterns such as therapy changes, medication compliance and recurrence relationship, and risk of adverse outcomes during maintenance phase
 - The choice of antidepressant, average length of new treatment maintenance, average number of co-administered medications (e.g., atypical antipsychotics, mood stabilizer, thyroid hormone, psychostimulant) when following changes occur from initial monotherapy:
 - Switching
 - Combination
 - Augmentation
 - Medication compliance and recurrence
 - Compliance measured as adherence and persistence
 - Recurrence
 - Relationship between recurrence and compliance

PFIZER CONFIDENTIAL

- *Risk of adverse outcomes measurement between individual ADs that are well known to be treatment-related (e.g., hyponatremia, GI bleeding, fractures, falls, risk of intracranial hemorrhage, attempted suicide/self-harm, myocardial infarction, epilepsy/seizures, stroke/transient ischemic stroke)*

Secondary objectives:

1. *Choice of antidepressants and drug utilization patterns in patients with various comorbidities*
 - *Psychiatric comorbidities*
 - *Mild cognitive impairment (MCI)*
2. *The relationship of non-pharmacologic treatment and discontinuation, medication compliance*
 - *Non-pharmacologic treatments may include: cognitive behavioral therapy (CBT), frequency of physician visit during acute and maintenance phase of treatment*
 - *Frequency of visit during the first 3 months of acute phase and its relationship to treatment maintenance at 4, 5, 6, 7, 8, 9 month time points and discontinuation rate*
3. *Choice of antidepressants by non-psychiatric specialty*

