7.2.3 Patients with Depression and Comorbidity Analysis

- To understand the antidepressant choice among Korean patients with depression and other comorbidities (psychiatric comorbidities or mild cognitive impairment (MCI))
- Secondary analysis
- Endpoints:
 - Proportion of 11 antidepressants
 - Choice of study drug
- Population: patients who satisfy the acute treatment phase population and with a prespecified comorbidity
- Significance on continuous variables will be tested by ANOVA (if equal variance condition satisfied) or Kruskal-Wallis H test (otherwise). Provider specialty and other patient characteristics will be used to fit antidepressant choice by multivariate logistic regression analysis of each study drug choice.
- Covariates: antidepressant class covariates such as SSRIs, SNRIs, other ADs will be used as grouping variables.
- Missing values will be dropped from the analysis.

- The role of this analysis is to provide information on antidepressant selection in the acute phase of drug therapy for Korean patients with depression and comorbidity by each comorbidity group.

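### SAP 7.2.5 restricts the specialty analysis to patients with a comorbidity, which contradicts secondary objective 3, the section's own endpoint and protocol 9.7

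*SAP*

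**What the plan says.** Secondary objective 3, in protocol section 8 and SAP 2.2, is "Choice of antidepressants by non-psychiatric specialty". Both documents follow it with a list of specialties (rheumatology, cardiology, urology and others). Neither attaches a comorbidity condition.

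SAP 7.2.5 carries out this objective. Its purpose is "To understand the antidepressant choice among the Korean providers by specialty" and its only endpoint is "Proportion of 11 antidepressants by provider specialty". The population line then adds a condition: "Population: patients who satisfies the acute treatment phase population and with a prespecified comorbidity". The closing role sentence says the analysis informs on "antidepressant selection in the acute phase of drug therapy for Korean patients with depression and comorbidity by each comorbidity group" and does not mention specialty.

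For proportions of the study drugs, protocol 9.7 states: "The proportions and drug utilization patterns comparisons of 11 study drugs will use all the patients satisfying inclusion and exclusion criteria (raw data". Protocol 9.9 presents the analysis of prescriptions from other specialists as a way to identify practice patterns in those specialties, again with no comorbidity condition.

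**The concern.** The objective asks what each specialty prescribes to eligible patients. The population line answers a narrower question: what each specialty prescribes to those eligible patients who also have a listed comorbidity. An analyst who applies the line filters the cohort and reports proportions that do not describe the specialty's eligible patients. An analyst who ignores it departs from the SAP.

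This matters because 7.2.5 is the only section that commits to drug proportions by specialty. If it runs in the subset, no planned output answers objective 3 in the population that the objective and protocol 9.7 describe.

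**Working it through.** The documents give no sample size, prevalence or drug share for this analysis, so there is no plan figure to reproduce. The check is a comparison of texts, followed by an algebraic statement of the consequence.

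**Step 1. Compare the secondary analyses.**

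| SAP section | Subject | Population | Role sentence |
|---|---|---|---|
| 7.2.3 | Drug choice in comorbid patients | Acute-phase population with a comorbidity | By comorbidity group |
| 7.2.4 | Non-pharmacological treatment and compliance | Acute-phase population, no restriction | Matches its subject |
| 7.2.5 | Drug choice by specialty | Acute-phase population with a comorbidity | By comorbidity group |

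The population line in 7.2.3 is "Population: patients who satisfy the acute treatment phase population and with a prespecified comorbidity". The line in 7.2.5 differs only in one verb ending. The role sentences of the two sections are the same, and both end "for Korean patients with depression and comorbidity by each comorbidity group". In 7.2.3 these lines fit the subject. In 7.2.5 they do not.

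**Step 2. Look for a stated reason.** The change table in SAP section 1 covers the data period, the age limit, MPR, persistence, adherence and recurrence. It has no entry on the specialty analysis. SAP 4.4 lists comorbidities and prescriber specialty as separate subgroup factors, not as nested ones. Nothing in either document explains the restriction.

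**Step 3. Ask who is dropped.** Section 7.2.5 does not define the qualifying comorbidity. Section 7.2.3 names psychiatric comorbidities or mild cognitive impairment. The comorbidity row of SAP Table 3 also lists the Charlson index. On any of these readings, patients with no qualifying condition are excluded. Which patients those are depends on the reading.

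**Step 4. Express the consequence.** For one drug in one specialty, let f be the share of patients with a qualifying comorbidity, and let p_c and p_n be the drug's share among comorbid and other patients.

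- All-patient share: f × p_c + (1 − f) × p_n
- Share under 7.2.5 as written: p_c
- Difference: (1 − f) × (p_c − p_n)

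The difference is zero only if f = 1 or if p_c = p_n. Table 3 itself says that the listed comorbidities may affect how antidepressants are used, so p_c = p_n cannot be taken for granted.

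**Step 5. Illustrate, with assumed inputs.** Take p_c − p_n = 10 percentage points. This value and the values of f are assumptions and come from neither document.

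- f = 0.3: 0.7 × 10 = 7 points
- f = 0.5: 0.5 × 10 = 5 points
- f = 0.7: 0.3 × 10 = 3 points

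Comparisons between specialties can be affected too. Suppose two specialties share the same p_c and p_n, but f is 0.3 in one and 0.7 in the other. Their all-patient shares differ by (0.7 − 0.3) × 10 = 4 points, while the restricted analysis shows no difference.

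**The case against.** The best defence is that this is a visible drafting slip. The title, purpose and endpoint of 7.2.5 all name the right target, and the two wrong lines are recognisably those of 7.2.3. A sensible analyst could resolve the conflict from protocol 9.7. Specialty also enters elsewhere without a comorbidity filter: SAP 7.2.1 uses it to model drug choice in the section 4.1 cohort, and 4.4 allows subgroup analysis by prescriber specialty. The analysis is secondary, and SAP section 3 declares no hypotheses or decision rules.

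Much of this stands. Carried-over text is the likeliest explanation, the harm arises only if the line is programmed literally, and no primary endpoint is touched. Two parts do not stand. The population line is the operative rule, and the role sentence supports it, so a reader could take the restriction as intended. The other sections also do not fill the gap: 4.4 is optional, and 7.2.1 gives a regression rather than drug proportions by specialty.

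It could also be said that protocol 9.7 cannot forbid every subset, since objective 1 needs comorbid patients. That is true, but objective 1 names its subset, and objective 3 names only specialty.

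**Conclusion.** The contradiction is real and sits in operative text. As written, the only committed analysis of drug proportions by specialty would run in a selected subset. This conflicts with objective 3, with the purpose and endpoint of 7.2.5, and with protocol 9.7. The direction and size of the error cannot be determined from the documents. The 3 to 7 points shown above rest wholly on assumed inputs.

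A reader might infer more than the documents support:

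- **That every patient without a psychiatric or cognitive code is dropped.** This borrows the definition in 7.2.3. Section 7.2.5 leaves the term undefined, and Table 3 includes the Charlson index.
- **That the retained patients are atypical of non-psychiatric practice, or that specialties which seldom code psychiatric conditions lose more.** Neither is shown. The Table 3 list is broad (sleep, adjustment, anxiety and somatoform disorders, dementia), and comorbidity is taken from medical claims without limiting it to the prescriber's own coding.
- **That a particular fraction of patients or prescriptions is lost.** No prevalence is given, and a loss of patients is not in itself a bias in drug shares.
- **That the flaw is critical to the study.** It affects a secondary descriptive analysis.

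The appropriate rating is should-fix.

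**What to change.** In SAP 7.2.5:

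1. Set the population to patients who satisfy the acute treatment phase population, as 7.2.4 does, with no comorbidity condition.
2. Rewrite the role sentence so that it refers to antidepressant selection in the acute phase by provider specialty.
3. If a comorbidity-restricted version is also wanted, keep it only as a labelled subgroup and define the qualifying comorbidities.

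If the sponsor did intend the restriction, the SAP should justify it and reconcile it with objective 3 and protocol 9.7.

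The fix should not add a rule that classifies patients by the specialty of the index prescriber. Table 3 defines drug proportions over prescriptions in the first 90 days, and protocol 9.9 speaks of prescriptions from other specialists. A patient-level index rule could therefore misattribute later prescriptions.

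The cost is two SAP sentences. The unrestricted cohort is the one already used for 7.2.1, so no new data are needed. The SAP was amended during data analysis, so the tables by specialty need rerunning only if the filter has already been programmed.
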